4.3 Post Marketing Requirement [Impavido NDA, 2014]

4.2.1 FDA Post-Marketing Requirement # 2127-4:

“Conduct a descriptive study regarding efficacy outcome and adverse reactions in patients with leishmaniasis who weigh more than 75kg.”

Final Protocol Submission: March 2015
Interim Report Submission: March 2016
Interim Report Submission: March 2017
Interim Report Submission: March 2018
Interim Report Submission: March 2019
Study Completion: March 2020
Final Report Submission: March 2021”

4.3.2 Previous Advice from the FDA Concerning this Requirement

“**Conduct a descriptive study regarding efficacy outcome and adverse reactions in patients with leishmaniasis who weigh more than 75kg.** This study should cover the period of five years following drug approval. Patient demographics (including age, weight, sex, race, prior medications, geographic area where *Leishmania* infection was acquired and immune status), total daily dosage of Impavido and mg/kg dosage received, treatment duration and site of infection should be described. Efficacy outcome and adverse reactions should be described. Yearly reports summarizing this data should be submitted.” (information request of 24 Jan 2014)

4.4 Rationale for Protocol

In an operational sense, the purpose of this protocol is to fulfill post-marketing requirement 2127-4 in accord with the specifics of the information request of 24 Jan 2014.

In a scientific sense, the purpose of this protocol is to provide as much data as possible on the possible relationship of lower mg/kg daily doses of miltefosine and efficacy.

For these purposes, a Higher-weight Patient Registry will be instituted and maintained from March, 2015 to March, 2020.

5 STUDY OBJECTIVES

Implement a higher-weight-patient registry for Impavido in the US for the time period March, 2015 to March 2020.

6 STUDY DESIGN

This study is a prospective observational study in which patients undergoing treatment for leishmaniasis with Impavido in the US and who weigh > 75 kg can volunteer to provide information about their clinical response to treatment up to 6 months after the start of treatment.

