2 STUDY SCHEDULE OF ASSESSMENTS

Parameter	Study Time Period				
	Screening	End of Treatment Period	1 Month Post Treatment	3 Months Post Treatment	6 Months Post Treatment
Consent	X				
Demographics (gender/age/weight/race)	X				
Leishmaniasis Hx	X				
Concomitant Diseases	X	X			
Miltefosine treatment	(a)	X			
Clinical Laboratory Tests	X (b,c)	X(b,c)	X (c)	X (c)	X (c)
Concomitant Medications	X	X			
Adverse Events	X	X			
Efficacy		X	X	X	X

(a): Patients may contact the Registry after having been administered at least one dose of miltefosine
 (b): AST and creatinine at screening and end of treatment; white blood cells (WBC), hemoglobin, and platelet count for patients with VL at all time

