3 SYNOPSIS

Impavido® (miltefosine) was approved in the United States (US) in March 2014 for the treatment of visceral, cutaneous, and mucosal leishmaniasis due to specified *Leishmania* species. Impavido is the first drug approved in the US for cutaneous or mucosal leishmaniasis, and is the only oral drug worldwide that is generally effective for the leishmaniases.

Since oral miltefosine is administered at 2 capsules for day to patients of 30-44 kg and 3 capsules per day to patients > 44 kg, in each weight bracket, higher weight patients will receive less drug on a mg/kg basis than lighter patients. For example, patients who weigh 45 kg and receive 3 capsules per day will receive 3.3 mg/kg/day whereas patients who weigh 90 kg and receive 3 capsules will receive 2.0 mg/kg/day.

Whether higher-weight US patients will have efficacy rates that are lower on an absolute basis is unknown.

Objective: The purpose of this observational study is to fulfill PMR 2127-4: implement a higher-weight-patient registry for the time period Mar 2015-Mar 2020.

Study Design: This study is a prospective observational study in which patients undergoing treatment for leishmaniasis with Impavido in the US and who weigh > 75 kg can volunteer to provide information about their clinical response to treatment up to 6 months after the start of treatment.

Population: Leishmaniasis patients treated with Impavido who weigh more than 75 kg.

Drug Product:

Drug name: Impavido (50 mg capsules).

Dosing regimen: as per the Impavido Product Label

Study Procedures: Patients who weigh more than 75 kg will become aware of the Impavido Higher-Weight Patient Registry via the Impavido website. By calling [name], the patient will be connected to the Impavido Higher-Weight Patient Registry Coordinating Center. A trained staff member will acquaint the patient with the goals and procedures of the study. If the patient tentatively agrees to participate in the study over the telephone, the patient will be mailed information forms, the Consent/Assent Forms, and the Consent for the patient's physician to release medical information. Receipt of the two signed Consent and/or Assent Forms by the Coordinating Center will signify patient consent. The Coordinating Center will contact the patient's physician at the end of treatment, and at 1, 3, and 6 months after completing treatment, to collect data on efficacy and adverse effects (only during treatment).

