9 PROCEDURES

Parameter	Study Time Period				
	Screening	End of Treatment Period	1 Month Post Treatment	3 Months Post Treatment	6 Months Post Treatment
Consent	X				
Demographics (gender/age/weight/race)	X				
Leishmaniasis Hx	X				
Concomitant Diseases	X	X			
Miltefosine treatment	(a)	X			
Clinical Laboratory Tests	X (b,c)	X(b,c)	X (c)	X (c)	X (c)
Concomitant Medications	X	X			
Adverse Events	X	X			
Efficacy		X	X	X	X

(a): Patients may contact the Registry after having been administered at least one dose of miltefosine
 (b): AST and creatinine at screening and end of treatment;
 (c): White blood cells (WBC), hemoglobin, and platelet count for patients with VL at all time

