9.4 Outcomes

The Impavido Higher-Weight Patient Registry Coordinating Center will contact the patient's physician at the end of the treatment period, and at 1, 3, and 6 months after the end of therapy, and request that the relevant data forms be completed and submitted.

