10.2 Treatment Data

Miltefosine Treatment Regimen

Daily dose in mg, dose in mg/kg, duration of therapy

Adverse events

Symptoms: gastrointestinal, other
Laboratory parameters (if available)

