10.3 Efficacy Data at 1, 3, and 6 months

- VL : Spleen size
Hemoglobin, platelets, white cell count
- ML: Symptoms, physical status at original site of infection
- CL : Lesion characteristics: ulcer, nodule, plaque, scab
Lesion size: Approximate size [length x width in inches, cm, or fingerwidths]

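### Does the start-of-treatment wording in section 6 cut off the final 6-month efficacy contact?

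*Protocol*

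**What the plan says.** Two places count follow-up from the start of treatment. Section 6 says that patients "can volunteer to provide information about their clinical response to treatment up to 6 months after the start of treatment". The Synopsis, under Study Design, repeats the limit: "up to 6 months after the start of treatment".

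The rest of the protocol counts from the end of treatment:

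- The Synopsis, under Study Procedures, has the Coordinating Center contact the physician "at the end of treatment, and at 1, 3, and 6 months after completing treatment, to collect data on efficacy" and on adverse effects.
- Section 9.4 sets the contacts "at the end of the treatment period, and at 1, 3, and 6 months after the end of therapy".
- The schedules in sections 2 and 9 both end with a column headed "6 Months Post Treatment", with Efficacy marked. They also mark Efficacy in the end-of-treatment column.

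The data list in section 10 is less complete. Section 10.3 is headed "Efficacy Data at 1, 3, and 6 months", with no anchor and no mention of end of treatment. Section 10.2 covers the regimen ("Daily dose in mg, dose in mg/kg, duration of therapy") and adverse events, but has no efficacy item.

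**The concern.** Start and end of treatment are different anchors. They differ by the length of treatment, so the two sets of statements conflict whatever convention is used for a month, and the Synopsis conflicts with itself. If section 6 were applied as a limit, the last efficacy observation in the study would fall outside it. That would hurt a registry that expects only 3 to 10 patients a year and whose stated scientific aim (section 4.4) is to gather as much data as possible on mg/kg dose and efficacy.

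The section 10.3 heading raises a second worry. Someone who designed the data forms from section 10 alone might leave efficacy fields off the end-of-treatment form.

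**Working it through.** **Size of the difference in anchor.** Inputs: the 28-day course given in section 4.2.4 for patients of 45 kg or more, which includes everyone above 75 kg, and an assumed average month of 30.44 days.

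| Point in time | Calculation | Day from first dose |
|---|---|---|
| Window counted from start closes | 6 × 30.44 | about 183 |
| 1-month contact | 28 + 30.44 | about 58 |
| 3-month contact | 28 + 3 × 30.44 | about 119 |
| 6-month contact | 28 + 6 × 30.44 | about 211 |

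Gap: 211 − 183 = 28 days, which is simply the treatment duration. Time left after the last dose under the section 6 wording: 183 − 28 = 155 days, and 155 / 30.44 = 5.1 months. The 1- and 3-month contacts fall inside the window and the 6-month contact falls outside it. The gap is shorter if treatment stops early and longer if it is interrupted or extended.

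**Which wording governs collection.** The Coordinating Center acts on section 9.4 and the schedules: it contacts the physician at the listed times and asks for the forms. All of these count from the end of treatment. Section 6 is one permissive sentence about what volunteers may do. It sets no visit window, no exclusion and no instruction to discard later data.

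**Which wording governs analysis.** Section 11.2 analyses data for all eligible subjects and defines eligibility by at least one administration of the drug. Section 11.6 gives by-subject listings and summaries of the outcome data. Neither refers to a period counted from the start of treatment. Section 11.1 states that there is no hypothesis and no formal sample size calculation, so no power or error rate depends on the anchor.

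**End-of-treatment efficacy.** The schedules mark four efficacy time points (end of treatment, 1, 3 and 6 months) and the 10.3 heading names three. The missing one is required by the Efficacy mark in both schedules and by the Synopsis procedures, and section 9.4 provides the contact. For patients with VL, the footnote to the section 9 schedule also requires blood counts throughout: "White blood cells (WBC), hemoglobin, and platelet count for patients with VL at all time". The other items (spleen size, mucosal symptoms and physical status, lesion characteristics and size) are covered by the Efficacy mark itself. Their content is not in doubt, because sections 10.1 and 10.3 list the same disease-specific items for VL, ML and CL.

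**The case for a change.** The best case for a change is that the protocol does contradict itself on a matter it chose to state, so this is not something left to a statistical analysis plan. The correction would be cheap: two sentences and one heading, with no new contact. The Coordinating Center prepares the forms (section 14.3), and section 10 is the natural place to look for their content. Yearly reports on so few patients should rest on one stated set of time points.

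The inconsistency stands, and so does the arithmetic. The step to a practical consequence does not. Whoever builds the forms also has two identical Efficacy rows and section 9.4, and would have to overlook all of them to leave out the end-of-treatment assessment. A coordinator who follows section 9.4 collects the 6-month data, and nothing in section 6 or section 11 tells anyone to drop them. The agreement among the operative sections also settles which anchor is meant, so different readers should not reach different answers.

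**Conclusion.** This is a clerical slip with no effect on the data or the analysis, and no change to the plan follows. The wording differs by the length of treatment, about 28 days for a full course, and the 10.3 heading omits one of four scheduled efficacy time points. Both schedules, section 9.4 and the Synopsis procedures agree on the intended follow-up, and the descriptive analysis uses whatever those contacts yield.

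This conclusion assumes that the registry runs on the schedules and section 9.4, as the protocol directs, and that the data forms, which are not shown, follow the Efficacy marks. A month of 30.44 days is also assumed, but it affects only the day counts.

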7 STUDY SUBJECTS

7.1 Estimated Number of Subjects

Estimated 3-10 per year.

7.2 Inclusion Criteria

To be eligible for the study, the following must be answered “YES”:

1. Did the subject give consent to collect data from her or her physician?
2. Was the subject treated for leishmaniasis with miltefosine?
3. Does the subject weigh more than 75 kg?

8 DRUG PRODUCT

Impavido (capsules of 50 mg strength) obtained through purchase in the US.

8.1 Storage and Administration

Appropriate storage and administration of Impavido in accord with the Product Label is the responsibility of the patient.

Storage and administration data will be recorded on appropriate pages of the data form.

8.2 Concomitant Therapy

All concomitant medications will be recorded on the data form.

9 PROCEDURES

Parameter	Study Time Period				
	Screening	End of Treatment Period	1 Month Post Treatment	3 Months Post Treatment	6 Months Post Treatment
Consent	X				
Demographics (gender/age/weight/race)	X				
Leishmaniasis Hx	X				
Concomitant Diseases	X	X			
Miltefosine treatment	(a)	X			
Clinical Laboratory Tests	X (b,c)	X(b,c)	X (c)	X (c)	X (c)
Concomitant Medications	X	X			
Adverse Events	X	X			
Efficacy		X	X	X	X

(a): Patients may contact the Registry after having been administered at least one dose of miltefosine
 (b): AST and creatinine at screening and end of treatment;
 (c): White blood cells (WBC), hemoglobin, and platelet count for patients with VL at all time

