9.1 Subject Recruitment

Patients will be alerted to the Impavido Higher-weight-patient Registry availability via the Impavido website which will supply a toll free number ([name]) to call.

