9.3 Screening Procedures

Physician will complete data form sections relevant to demographics, history of leishmaniasis, history of Impavido treatment (if any), pre-treatment clinical laboratory tests [aspartate aminotransferase (AST), creatinine, and if the patient has VL WBC, hemoglobin, and platelet count], concomitant diseases, concomitant medications.

From this information, eligibility to participate in the Higher-Weight Patient Registry will be determined.

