11.2 Analytical Populations

Data for all eligible subjects will be analyzed. An eligible subject is anyone who received at least one administration of Impavido for leishmaniasis.

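### The registry is described as prospective in patients on treatment, but its entry rules also admit volunteers who have finished treatment and know their response

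*Protocol*

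**What the plan says.** The design statement in Protocol section 6, repeated in the synopsis (section 3), reads: "This study is a prospective observational study in which patients undergoing treatment for leishmaniasis with Impavido in the US". Section 9.4 has the Coordinating Center approach the physician "at the end of the treatment period, and at 1, 3, and 6 months after the end of therapy", which works as planned only if the subject joined before treatment ended.

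The rules that decide who enters and who is analysed are worded differently:

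- Section 7.2, criterion 2: "Was the subject treated for leishmaniasis with miltefosine". Criterion 3: "Does the subject weigh more than 75 kg". Criterion 1 concerns consent. None sets a time limit.
- Footnote (a) to the schedule (sections 2 and 9): "Patients may contact the Registry after having been administered at least one dose of miltefosine". This is an earliest time, with no latest time.
- Section 11.2: "An eligible subject is anyone who received at least one administration of Impavido for leishmaniasis". All such subjects are analysed.

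Recruitment is by self-referral (section 9.1): "Patients will be alerted to the Impavido Higher-weight-patient Registry availability via the Impavido website". The synopsis and section 11.6 promise by-subject and overall presentations of outcomes and do not mention time of entry.

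**The concern.** Section 4.4 gives the scientific purpose as data on how efficacy relates to lower mg/kg doses. A patient who finds the website after finishing the course may decide to call because the lesion healed, because it did not, or because of side effects. Once the outcome can influence who volunteers, the pooled cure and adverse-event percentages no longer describe only subjects followed forward, although the study is labelled prospective. A reader of the summaries could not be sure of telling the two kinds of subject apart.

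The study is descriptive (section 11.1 states that it has no hypothesis), so no error rate or power is affected. What is at stake is what the percentages mean.

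**Working it through.** The protocol gives no calculated figure to reproduce. The check sets its statements side by side and then works out timing and the weight of one subject.

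**1. Do the rules exclude a late entrant?** Take a patient above 75 kg who completed the course, had a 3-month check, then found the website, called, and returned both signed forms.

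| Rule | Met? |
|---|---|
| 7.2 criterion 1 (consent) | yes |
| 7.2 criterion 2 (was treated) | yes |
| 7.2 criterion 3 (weight) | yes |
| Footnote (a) (at least one dose before contact) | yes |
| 11.2 (at least one administration) | yes |

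Only the descriptive wording of sections 3 and 6 and the sequence in the schedule and section 9.4 point the other way. None of these is an eligibility rule.

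**2. What is already known at late entry?** Inputs: a 28-day course (section 4.2.4); efficacy scheduled at end of treatment and at 1, 3 and 6 months after it (sections 2 and 9); adverse effects collected only during treatment (section 3). Assumption: one month is 30 days. Days from first dose: 28; 28 + 30 = 58; 28 + 90 = 118; 28 + 180 = 208.

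| First contact after day | Scheduled efficacy assessments already past | Adverse-event period over |
|---|---|---|
| 28 | 1 of 4 | yes |
| 58 | 2 of 4 | yes |
| 118 | 3 of 4 | yes |
| 208 | 4 of 4 | yes |

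Section 10.3 lists efficacy data only at 1, 3 and 6 months. On that count the figures are 0, 1, 2 and 3 of 3.

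**3. Weight of one subject.** Section 3 expects 3 to 10 patients a year for 5 years: 3 × 5 = 15 to 10 × 5 = 50. Each subject carries 100/15 = 6.7 to 100/50 = 2.0 percentage points.

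If k of n subjects enter late, then

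pooled % − % in the others = (k/n) × (late % − other %),

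so the gap is at most k/n in absolute value. For k = 1 that is 6.7 points (n = 15) or 2.0 points (n = 50). The bound is reached only if the two groups differ by the full 100 points.

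**4. Can the direction be told?** Illustration only; the share s of late entrants and the ratio r, by which cured patients volunteer more readily than failures, are assumptions with no source in the protocol. With true cure rate p, a late entrant is a cure with probability pr/(pr + 1 − p), and the pooled shift is s × [pr/(pr + 1 − p) − p]. Take p = 26/38 = 68.4% (counts of the lowest dose group in Table 2, section 4.2.5) and s = 25%:

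- r = 0.5: 0.25 × (0.520 − 0.684) = −4.1 points
- r = 1: 0
- r = 3: 0.25 × (0.867 − 0.684) = +4.6 points

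The sign depends entirely on r, which the protocol does not inform.

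**The case against.** The strongest reply is that the text, read as a whole, shows the intended window. The design statement limits volunteers to patients on treatment. The schedule puts consent and screening before the end-of-treatment column. Section 9.3 collects pre-treatment laboratory values, and Impavido history only where there is some. Footnote (a) sits in the screening column and can be read simply as letting a patient who has begun dosing still join. This is fair evidence of intent, and a reader should not infer that the protocol plans retrospective enrolment. It does not supply the missing limit: criterion 2 and section 11.2, which staff and analysts will apply, contain none.

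Three further objections stand in part:

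- **The analysis.** That outcomes will be pooled regardless of entry time is partly an inference from silence. A statistical analysis plan, not shown, could add a split, and by-subject presentation is promised. The conflict over who may enter remains a protocol matter.
- **The dates.** One might infer that timing will not be captured. The protocol does not show that. Administration data go on the data form (section 8.1), consents are mailed to the Coordinating Center (section 9.2), and the follow-up contacts need an end-of-therapy date (section 9.4). First and last dose dates are largely form-level detail. The date of first contact, however, is not named in section 10.
- **The population.** Section 11.2 omits the weight and consent criteria, so one might infer that subjects of 75 kg or less, or without consent, would be analysed. Section 7.2 governs entry, and such patients should have no registry data. No effect on results is shown.

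**Conclusion.** The point holds as a conflict between the stated design and the operative rules. Nothing in section 7.2, footnote (a) or section 11.2 requires entry before treatment ends, so a volunteer whose response is already known can qualify and be pooled with subjects followed forward. With 15 to 50 expected subjects, each carries 6.7 to 2.0 percentage points of a pooled percentage. The assessment days rest on a 28-day course and 30-day months.

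A reader might go further and infer that the reported cure rate will be inflated. The protocol does not support that: it gives no basis for the number of late entrants or for the size or direction of any bias, and the illustration changes sign with an assumed ratio. The defect is worth correcting because the correction is cheap; it does not invalidate the registry.

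**What to change.** 1. Reconcile sections 2, 3, 6, 7.2, 9 (footnote a) and 11.2 on whether entry after the end of treatment is allowed. If it is not, state the limit in section 7.2 and the footnote.
2. If it is allowed, add the date of first contact to section 10.1. First contact serves better than receipt of consent, because the forms travel by mail and a patient who called during treatment could otherwise be classed as late.
3. In that case, in section 11.6 keep the all-subject summaries and also show efficacy and adverse events separately for first contact before and after the end of treatment. One cut-point is enough, since the schedule's first efficacy assessment is at the end of treatment. In the by-subject listing, flag which efficacy assessments preceded first contact. No subject is excluded.
4. In section 11.2, refer to subjects meeting section 7.2. This only aligns the wording.

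The cost is one date field and small denominators in the split tables: in a group of 5, each subject carries 100/5 = 20 points. The split makes entry time visible. It does not remove self-selection through the website, and a patient who joins during treatment may already know early side effects.

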9.1 Subject Recruitment

Patients will be alerted to the Impavido Higher-weight-patient Registry availability via the Impavido website which will supply a toll free number ([name]) to call.

